1) Primary To compare rates of the composite of any AF-related emergency department visit or unplanned CV hospitalization between Intervention and Usual care over 12 months	composite of any AF-related emergency department visit or unplanned CV hospitalization over 12 months	Intervention better than Usual Care	Generalized Estimating Equations (GEE) or frailty models
2) Secondary To compare I vs UC over 12 months on the following: any AF-related emergency department visit	any AF-related emergency department visit	Intervention better than Usual Care	GEE or frailty models
unplanned CV hospitalization	unplanned CV hospitalization	Intervention better than Usual Care	GEE or frailty models
strokes	strokes	Intervention better than Usual Care	GEE or frailty models
systemic embolism / major bleeding	systemic embolism / major bleeding	Intervention better than Usual Care	GEE or frailty models
mortality	mortality	Intervention better than Usual Care	GEE or frailty models
anticoagulant therapy	anticoagulant therapy	Intervention better than Usual Care	GEE or frailty models
access to specialist consultation	access to specialist consultation	Intervention better than Usual Care	GEE or frailty models
echo	echo	Intervention better than Usual Care	GEE or frailty models

catheter ablations	catheter ablations	Intervention better than	GEE or	frailty models
		Usual Care		
EQ5D	EQ5D	Intervention better than	GEE or	frailty models
		Usual Care		
health care costs	health care costs	Intervention better than	GEE or	frailty models
		Usual Care		
3) Subgroup Analyses:				
To compare the effect of I				
vs UC by different	All primary and	Effects on outcomes	Regres	sion methods with
subgroups: location of	secondary outcomes	differ by location of	approp	riate interaction
practice, patient sex,		practice	term	
age, CHADS2, CHADS-				
VASC, hypertension,				
diabetes and years of				
practice of family doctor				
4) Sensitivity Analyses:	composite of any	Results will remain	i)	patient-level
i) To assess the robustness	AF-related	robust		methods such as
of the results to different	emergency			random-intercept
methods of adjusting for	department visit or			model and
clustering;	unplanned CV			cluster-level [i.e.
ii) To assess the robust	hospitalization			random- and
ness of the results if the				fixed-effects
outcome is treated as the				meta-analytic]
count (number of events)			ii)	GEE using
				Poisson
				distribution

IMPORTANT REMARKS:

- The GEE is a technique that allows to specify the correlation structure between patients within a hospital and this approach produces unbiased estimates under the assumption that missing observations will be missing at random. An amended approach of weighted GEE will be employed if missing observations are found not to be at random.
- In all analyses results will be expressed as coefficient, standard errors, corresponding 95% and associated p-values.
- Goodness-of-fit will be assessed by examining the residuals for model assumptions and chi-squared test of goodness-of-fit.

Table 2. Characteristics of the Study Populations at Baseline

Characteristic	haracteristic Variable		Usual Care (N=543)	
Age – years Median Interquartile range	Age at start			
Male sex - n (%)	Sex (Male)			
Height – cm - Mean (SD)	Height			
Weight – Kg- Mean (SD)	Weight			
Urban location of care - n (%)	Location			
Heart rate – BPM - Mean (SD)	Heart Rate			
Systolic Blood pressure - mmHg Median Interquartile range	Systolic BP			
Systolic Blood pressure - mmHg Median Interquartile range	Diastolic BP			
Type of atrial fibrillation - n (%)				
Paroxysmal	AF Classification (Paroxysmal)			
Persistent	AF Classification (Persistent/Chronic)			
Newly diagnosed/new onset	AF Classification (First Episode)			
PREVIOUS MEDICATION USE - n (%)				
Aspirin	Ingredient (Aspirin)			
other antiplatelet	Ingredient (TICLOPIDINE) or (PRASUGREL) or (TICAGRELOR) or (CLOPIDOGREL)			
Vitamin K antagonist (Warfarin)	Ingredient (Warfarin)			
Non-vitamin K antagonist (NOAC)	Ingredient (DABIGATRAN) or (RIVAROXABAN) or (APIXABAN)			
Beta-blocker	Ingredient (TIMOLOL) or (LABETALOL) or (CARVEDILOL) or (PINDOLOL) or (ACEBUTOLOL) or (PROPANOLOL) or (NADOLOL) or (ATENOLOL) or (BISOPROLOL)			
Calcium channel blocker	Ingredient (NIFEDIPINE) or (FELODIPINE) or (AMLODIPINE) or (AMLODIPINE + ATROVASTATIN) or (DILTIAZEM) or (VERAPAMIL)			
Digoxin	Ingredient (DIGOXIN)			
Any other antiarrhythmic	Ingredient (DRONEDARONE) or (QUINIDINE) or (PROCAINAMIDE) or (MEXILETINE) or			

	(SOTALOL) or (LIDOCAINE) or (FLECAINIDE) or (PROPAFENONE) or (AMIODARONE)		
Nonsteroidal anti- inflammatory	Ingredient (SULINDAC) or (PETOPROPHEN) or (PIROXICAM) or (KETOROLAC) or (TENOXICAM) or (TIAPROFENIC) or		
	(INDOMETHACIN) and (ETODOLAC) or (NEPAFENAC) or (IBUPROFEN) or		
	(MELOXICAM) or (NAPROXEN) or (DICLOFENAC) or (CELECOXIB)		
OAC contraindication	OAC Contraindication (Yes)		
OAC other reason not prescribed	OAC reason not Rxd (Yes)		
BLEEDING AND STROKE RISK SCORES		'	
CHA ₂ DS ₂	NOT the value REPORTED in PCP chart.		
Score - Mean (SD) Score - n (%)	CALCULATED using documented RFs.		
0			
1			
2			
3 4			
5			
6			
7			
CHA ₂ DS ₂ -VASc	NOT the value REPORTED in PCP chart.		
Score - Mean (SD) Score - n (%)	CALCULATED using documented RFs.		
0			
1			
2			
3			
5			
6			
7			
8			
9 Bleeding risk: HAS-BLED			
Score - Mean (SD)			
Score - n (%)			
1			
2			
3 4			
5			
6			

7		
7 8		
9		
COEXISTING CONDITIONS - n		
(%)		
Previous stroke, systemic	Stroke (Yes) or SE (Yes) or TIA (Yes)	_
embolism or transient	Stroke (163) of 3E (163) of 11A (163)	
ischemic attack		
Congestive heart failure	HF/LV Dysfunction (Yes)	_
Hypertension	Hypertension (Yes) or (Yes-Treated) or (Yes-	
rrypertension	Not Treated)	
Diabetes mellitus	Diabetes (Yes-Not Documented) or (Yes-Type	
Diabetes memeas	1) or (Yes-Type 2)	
Previous myocardial	MI (MM-YYYY) or (ND)	
infarction	(
Vascular disease (any)	Vascular Disease (Yes)	
CAD	CAD (Yes)	
PAD/PVD	Aortic Plaque (Yes)	
UA	PAD/PVD (Yes)	
MI	UA (date) (MM-YYYY) or (ND)	
Aortic plaque	MI (date) (MM-YYYY) or (ND)	
Valvular Heart Disease	Replacement Type (Mechanical) or Mitral	
	Stenosis Type (Moderate) or (Severe)	
Congenial Heart Disease	Congenital Heart Disease (Yes)	
OSA	OSA Dx (Yes)	
Tobacco use		
Former	Tobacco use (Former)	
Current	Tobacco use (Current)	
Alcohol abuse	Alcohol abuse (Yes)	
Pericarditis	Pericarditis (Yes)	
Pulmonary Disease	Pulmonary Disease (Yes)	
INITEDVENITIONS (DDGGEDUDES		
INTERVENTIONS/PROCEDURES		
- n (%)	Vascular Procedure (Vas)	
Vascular procedure (any) CABG	Vascular Procedure (Yes) CABG (Yes)	
PCI	PCI (Yes)	
Ablation (for flutter or AF)	AF Ablation (Yes) or Previous Ablation for Aflu	_
Ablation from matter of All	(Yes)	
Pacemaker / ICD	Pacemaker (Yes)	
Cardioversion		
# of patients	Cardioversion (Yes)	
# of events – median (IQR)	Cardioversions no.	
Bleeding History - n (%)		

Any bleeding	Bleeding History (Yes)	
Intracranial	IC-Intracerebral (Yes) or IC-Other (Yes)	
Non-intracranial	NIC-Epistaxis (Yes) or NIC-GI (Yes) or NIC-	
Non intractation	Other (Yes)	
Major bleeding	Major bleeding (Yes)	
PAST REFERRALS - n (%)	major precumb (res)	
, ,		
AF Clinic	Referred to (AF Clinic)	
Cardiologist	Referred to (Cardiologist)	
Internist	Referred to (Internist)	
Electrophysiologist	Referred to (Electrophysiologist)	
Cath ablation	Referred to (Cath Ablation)	
ED visit for AF within the last		
12 months	ER Visits (Yes)	
# of patients - n (%)	ED Visits	
# of events - Mean (SD)	1	
	2	
	3	
	>3	
Cardiovascular-related		
hospitalization within the last		
12 months	CV Hospitalization (Yes)	
# of patients - n (%)	CV Hospitalizations	
# of events - Mean (SD)	1	
	2	
	3	
LAB VALUES)	
eGFR – ml/min	Value when Blood Work (eGFR)	
Median		
Interquartile range		
eGFR - n (%)		
< 30 ml/min		
30-50 ml/min		
> 50 ml/min		
Hemoglobin - g/L	Value when Bloodwork (Hemoglobin)	
Median	value when bloodwork (Hemoglobin)	
Interquartile range		
Platelet - µmol/L	Value when Bloodwork (platelet count)	
Median	value when bloodwork (platelet count)	
Interquartile range		
TSH - mIU/L	Value when Bloodwork (TSH)	
Median	Talle William Diodation (1911)	
Interquartile range		
INR		
CARDIAC ASSESSMENTS		 
Prior ECHO - n (%)	ECHO (Yes)	
Ejection Fraction	The calculated EF	
Licetion Fraction	THE CARCUIATED ET	

Patients with EF - n (%)		
EF -Mean (SD)		
Normal (≥ 51%)		
Slightly Reduced (41-50%)		
Moderately Reduced (31-40%)		
Severely Reduced (≤ 30%)		
Stress Test	Stress Test (Yes)	
Holder or Loop - n (%)	Holter (Yes) or Loop (Yes)	
ECG within 12 months	ECG (Yes)	

Table 3. Primary and Secondary outcomes at 12-months

Outcome (Usual Care is reference)	Interventio (N=		Usual Gro (N:	up	Primary analysis	Sensitivity analysis	
	No. of Patients	No. of Events	No. of Patients	No. of Events	HR (95% CI); p-value	IRR (95% CI), p-value	
Primary							
AF related ED visits or CV hospitalizations							
Secondary							
AF related ED visits							
Heart Failure							
Syncope/Presyncope							
TIA/Stroke							
ACS (UA/MI)							
Rate/Rhythm							
Unplanned CV							
hospitalization							
Heart Failure							
Syncope/Presyncope							
TIA/Stroke/SE							
ACS (UA/MI)							
Rate/Rhythm							
Stroke							
Ischemic							
Other							
All-cause mortality							

Table 4a: Sensitivity analysis using commonly used patient-level methods such as random-intercept model and meta-analytic cluster-level methods.

Outcome (Usual Care is reference)	Random- intercept model HR (95% CI), p- value
Primary	
AF related ED visits or	
CV hospitalizations	
Secondary	
AF related ED visits	
Unplanned CV hospitalization	

Table 5a Subgroup analysis and subgroup sensitivity analyses of primary efficacy composite Outcome

Sub-Group	HR (95% CI), Interaction term	IRR (95% CI),
(Usual Care is reference)	p-value	Interaction term p- value
Practice Location		
Rural		
Urban		
Patient Sex		
Female		
Male		
Age (years)		
<75		
≥ 75		
CHADS2		
0		
≥1		
CHADS-VASC		
0		
≥1		
Hypertension		
Yes		
No		
Diabetes		
Yes		
No		
Antithrombotics (baseline)		
Yes		
No		

Table 5b Subgroup analysis and subgroup sensitivity analyses of the number of AF Related ED Visits

Sub-Group	HR (95% CI), Interaction	IRR (95% CI),
(Usual Care is reference)	term p-value	Interaction term p-value
Practice Location		
Rural		
Urban		
Patient Sex		
Female		
Male		
Age (years)		
<75		
≥ 75		
CHADS2		
0		
≥1		
CHADS-VASC		
0		
≥1		
Hypertension		
Yes		
No		
Diabetes		
Yes		
No		
Antithrombotics (baseline)		
Yes		
No		

Table 5c Subgroup analysis and subgroup sensitivity analyses of number of CV Hospitalizations

Sub-Group	HR (95% CI), Interaction	IRR (95% CI),
(Usual Care is reference)	term p-value	Interaction term p-value
Practice Location		
Rural		
Urban		
Patient Sex		
Female		
Male		
Age (years)		
<75		
≥ 75		
CHADS2		
0		
≥1		
CHADS-VASC*		
0		
≥1		
Hypertension		
Yes		
No		
Diabetes		
Yes		
No		
Antithrombotics (baseline)		
Yes		
No

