The analysis and reporting of the trial results will follow the CONSORT Statement for cluster-randomization trials [129]. The baseline characteristics of the practices and patients will be reported by group as mean (standard deviation) or median (first quartile, third quartile) for continuous variables, depending on the distribution, and count (percent) for categorical variables. The analysis will follow the intention-to-treat (ITT) principle. The unit of randomization will be the practice. The unit of analysis will be the patient. We will use multiple imputation to handle missing data to enable ITT analysis. Multiple imputation is a Monte Carlo technique in which the missing values are replaced by $m > 1$ simulated versions, where 'm' is typically small. Each of the simulated complete datasets will be analyzed by standard methods, and the results will be combined to produce estimates and confidence intervals that incorporate missing data uncertainty [133]. We will use generalized estimating equations (GEE) – assuming exchangeable correlation structure for patients within the same practice, and adjusting for urban and rural practice types to analyse all outcomes [130]. Unlike ordinary regression techniques, GEE allows us to model the intra-practice correlation among patients within each practice. The results will be reported as the estimate of the effect, corresponding 95% confidence interval and associated p-values. All p-values will be reported to three decimal places with those less than 0.001 reported as $p < 0.001$. The criterion for statistical significance will be set a priori at $\alpha = 0.05$, and adjusted using the Bonferroni method for multiple secondary analyses. All analyses will be performed using SAS 9.4 (Cary, NC).

Sensitivity analyses: 1) There are several methods for analyzing cluster RCTs [131]. Therefore, we will perform sensitivity analyses using some of the commonly used patient-level methods such as random-intercept model and cluster-level (i.e. random- and fixed-effects meta-analytic) methods to assess the robustness of the results. 2) Given that the unit of randomization is the practice, there is a higher chance of potential imbalance of patient-level baseline characteristics. We will perform some sensitivity analysis to adjust for any potential imbalance.

HRQoL

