This statistical analysis plan follows the JAMA Guidelines for the Content of Statistical Analysis Plans in Clinical Trials ¹³. A summary of all planned analyses is provided in **Table 1**.

Blinded Analyses

All statistical analyses will first be completed using blinded treatment groups (i.e. treatment X and Y).

Presentation of Data

The trial results will be presented according to the CONSORT guidelines for randomized controlled trials (RCTs) 14 . The baseline demographic characteristics of the patients will be summarized by group, reported as a mean (standard deviation [SD]) or median (first quartile, third quartile) for continuous variables and count (percent) for categorical variables (**Tables 2**). All statistical tests will be 2-tailed with α =0.05.

Primary Outcome Analysis

The primary efficacy analysis will be an analysis to compare rates of the composite of any AF-related emergency department visit or unplanned CV hospitalization between Intervention and Usual care over 12 months, with the outcome being treated as number of events (Tables 3). The analysis will follow the intention-to-treat (ITT) principle. While the unit of randomization is the practice/physician, the unit of analysis will be the patient. We will use Generalized Estimating Equations (GEE) —assuming exchangeable correlation structure for patients within the same practice and adjusting for urban and rural practice types to analyze all outcomes¹⁵. Unlike ordinary regression techniques, GEE allows us to estimate the intra-practice correlation among patients within each practice. For time-to-event analysis this is done using frailty-models. The results will be reported as estimate of the effect—reported as hazard ratio [HR], corresponding 95% confidence interval and associated p-values. All p-values will be reported to three decimal places with those less than 0.001 reported as p<0.001. The criterion for statistical significance will be set a priori at alpha = 0.05. The answers to the five questions in the EQ-5D-5L will be converted to health utilities using the Canadian scoring algorithm¹⁶. Cost effectiveness analysis

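### The SAP's missing-data rule puts ordinary and weighted GEE under the wrong assumptions, and it drops the protocol's multiple imputation

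*SAP*

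**What the plan says.** - **SAP, Important Remarks under Table 1.** On GEE in general: "this approach produces unbiased estimates under the assumption that missing observations will be missing at random". The fallback follows directly: "An amended approach of weighted GEE will be employed if missing observations are found not to be at random". The same remark says that GEE "allows to specify the correlation structure between patients within a hospital".
- **SAP, Primary Outcome Analysis.** The model is GEE "assuming exchangeable correlation structure for patients within the same practice" and "adjusting for urban and rural practice types to analyze all outcomes". No other covariate is named. The section also states: "The analysis will follow the intention-to-treat (ITT) principle".
- **Protocol, section 3.9.** "We will use multiple imputation to handle missing data to enable ITT analysis". It goes on to describe combining results over the completed datasets.
- **SAP, elsewhere.** Imputation does not appear in the text, in Table 1 or among the sensitivity analyses. Those deal with the clustering method and with treating the outcome as a Poisson count. Appendix 1 is not in the text, but the SAP says that it holds outcome definitions.

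**The concern.** The rule has three errors.

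1. GEE adjusted for arm and urban/rural is not unbiased under missing at random in general. If missingness depends on other recorded variables, such as earlier ED visits or admissions, the treatment effect can be biased when that dependence differs by arm or when the effect varies with those variables.
2. Weighted GEE is a remedy for data missing at random given the variables in the weight model. It does not address not-at-random missingness.
3. The trigger cannot be applied, because observed data do not distinguish missing at random from not at random.

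An analyst following the text would regard unweighted GEE as safe throughout the missing-at-random case. The one remedy the SAP names for that case would be held back for a case it cannot repair. The protocol's imputation could be left out, with nothing to say which document governs.

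EQ-5D is the most exposed of the outcomes that Table 1 assigns to GEE, because it depends on patient questionnaires (Protocol 3.7.3). Follow-up also differs by arm. CDSS data add to capture in the intervention arm only (Protocol 3.7.3), and only that arm has the patient portal with feedback and reminders (Protocol 4.2).

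**Working it through.** The plan gives no figure on this point to reproduce. The design inputs come from Protocol 3.8: 537 patients per arm, ICC 0.05 and cluster size 9. They reproduce the stated sample size: 768.32 × (1 + 8 × 0.05) = 768.32 × 1.4 = 1,075.65. Everything about missingness below is an assumption.

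**Step 1. Is the rule right?** Take control risk 50%, intervention risk 40% and a baseline factor carried by half the patients (risks 0.70 and 0.30 in control, 0.60 and 0.20 in intervention). Retention is 95%, except 65% in intervention patients with the factor.

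- Observed intervention risk: (0.5 × 0.95 × 0.20 + 0.5 × 0.65 × 0.60) / (0.5 × 0.95 + 0.5 × 0.65) = 0.290 / 0.800 = 0.3625.
- Control stays at 0.50, so the estimated difference is 0.1375 instead of 0.10.
- With the same retention pattern in both arms: 0.4625 − 0.3625 = 0.10, no bias in the difference.
- With missingness depending on arm alone, the difference is also 0.10.

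Simulated estimates (300 trials, 120 practices of 9, true difference 0.10):

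| Missingness | Ordinary GEE | Weighted GEE | Multiple imputation |
|---|---|---|---|
| Completely at random | 0.104 | 0.104 | 0.103 |
| At random (arm and baseline factor) | 0.136 | 0.099 | 0.098 |
| Not at random (arm and outcome) | 0.187 | 0.174 | 0.174 |

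This is an illustration of the rule, not a forecast for the primary outcome.

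**Step 2. EQ-5D at a true null.** Assume 35% of patients have utility lower by a gap of 0.10 to 0.20, the rest have mean 0.85, 20% of the rest are missing, and SD is 0.20. Let h be the share of the lower-utility group that is missing.

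- Observed share s = 0.35(1 − h) + 0.65 × 0.80.
- Lower-utility share among the observed q = 0.35(1 − h) / s.
- Observed mean = 0.85 − gap × q.
- Variance of an arm mean = v[1 + (9s − 1) × 0.05] / (537s), with v = SD² + q(1 − q)gap².
- Two-sided error = Φ(−1.96 + r) + Φ(−1.96 − r), with r = bias / SE.

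Worked case, gap 0.20, h = 0.50 against 0.30:

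- s = 0.695 and 0.765; n = 373 and 411; q = 0.2518 and 0.3203.
- Means 0.79964 and 0.78595, so the bias is 0.0137.
- Variances 0.0475 × 1.263 / 373 = 0.000161 and 0.0487 × 1.294 / 411 = 0.000153. SE = √0.000314 = 0.0177.
- r = 0.77; two-sided error 12.1%.

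| h by arm | Bias (gap 0.10 to 0.20) | Bias / SE | Two-sided error |
|---|---|---|---|
| 30% v 30% | 0 | 0 | 5.0% |
| 35% v 30% | 0.0016 to 0.0032 | 0.10 to 0.18 | 5.1% to 5.4% |
| 40% v 30% | 0.0033 to 0.0065 | 0.20 to 0.37 | 5.5% to 6.6% |
| 50% v 30% | 0.0068 to 0.0137 | 0.41 to 0.77 | 7.0% to 12.1% |

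Over SD 0.15 to 0.25, the last row runs from 0.33 to 0.97 SE (6.3% to 16.2%).

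**Step 3. Do the remedies work?** Simulation of the largest case (400 replicates, gap 0.20, residual SD 0.20, model with arm and urban/rural, Monte Carlo SE of bias 0.0009):

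| Analysis | Bias | Rejection |
|---|---|---|
| Full data | 0.0009 | 6.0% |
| Ordinary GEE | 0.0144 | 14.0% |
| Weighted GEE, driver recorded | 0.0009 | 5.0% |
| Multiple imputation, practice random intercept, driver recorded | 0.0008 | 6.8% |
| Weighted GEE, driver unrecorded | 0.0143 | 13.8% |

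A second, independent simulation gave bias 0.014 with 11.5% rejection for ordinary GEE, and about 0 with 6.5% for weighted GEE.

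**Step 4. Primary outcome with near-complete capture.** Suppose 35% of patients have risk 0.70 and the rest 0.39 (overall 0.35 × 0.70 + 0.65 × 0.39 = 0.4985). With 1% of the rest missing and h = 4% against 2%, the bias is 0.0014. With 2% missing and h = 5% against 2%, it is 0.0022. That is 0.1 to 0.2 percentage points, against the protocol's 10-point target.

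**The case against.** **A kinder reading.** If at random was meant loosely as completely at random, the sequence is sound: ordinary GEE if so, weighted GEE if missingness is found to depend on recorded variables, which can be checked. The errors then shrink to one slip of terminology. The SAP does not say this, nor does it say at random given arm and urban/rural. On any of these readings the sentence has to be rewritten.

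**The harm is assumed.** No missingness rate, utility SD or subgroup gap is documented, and the milder rows barely move the error rate. Differential questionnaire response is not shown either: paper forms are available to everyone, portal use is optional, and nothing says that portal reminders concern questionnaires. This stands, and it limits what can be claimed about size.

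**Bonferroni.** Protocol 3.9 adjusts secondary analyses. Dividing 0.05 by the SAP's 11 listed outcomes (an assumed divisor) gives a nominal 0.45%, and the largest case then gives about 0.8% to 2.0%. But the SAP sets all tests at 0.05 and does not repeat the adjustment. Even with it, the relative inflation remains.

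**Silence is not withdrawal.** Nothing in the SAP cancels the protocol's imputation. That is true, but the SAP gives its own missing-data rule without it, so the analyst has two plans and no order of precedence.

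**Hospital for practice.** This is a wording slip that other text settles. It adds no weight.

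**Conclusion.** The concern holds; the SAP should be corrected. The rule is wrong as written, and the loss of multiple imputation is a real protocol-SAP inconsistency. Neither conclusion depends on how much data is missing.

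The consequence does depend on it. For EQ-5D it ranges from nothing, when missingness is equal by arm and the effect is constant, to 0.014 (0.77 SE at SD 0.20) in the most unequal case examined. For the primary outcome it is probably negligible, because charts, primary care records and hospital records are reviewed in both arms. That estimate is on the risk-difference scale, whereas the SAP reports hazard and rate ratios.

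The cost-per-QALY interval comes from a bootstrap, not from this GEE, and is outside this point. The protocol's adjustment for baseline imbalance is a sensitivity analysis only, so it does not alter the main model.

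**What to change.** In the Important Remarks of the SAP:

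- State that ordinary GEE is valid if data are missing completely at random or if missingness depends only on covariates in the model.
- Delete the trigger that relies on finding data not to be at random.
- Name the protocol's multiple imputation as the main missing-at-random method for outcomes analysed by GEE. The imputation model should respect practice clustering and use baseline variables already collected, such as earlier ED visits, earlier admissions, comorbidities and risk scores.
- Keep weighted GEE only as an alternative under missing at random, with its weight model specified.
- Replace hospital with practice.

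The cost is SAP wording and modest programming; no new data are needed. The choice should be fixed before unblinded results are seen. Missing data in the QALY bootstrap, censoring in any frailty model, and a delta-shift analysis of EQ-5D for not-at-random missingness are separate, optional points that this correction does not settle.
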